3.2.4. Progression-Free Survival (exploratory)

PFS is defined as the time from the date of randomisation to the date of disease progression (following disease recurrence) or death (from any cause in the absence of progression) (i.e. date of PFS event or censoring – date of randomisation + 1). The date of disease progression will be recorded by the investigator and defined according to local standard clinical practice including: objective radiological, symptomatic or other progression. Patients alive and for whom a disease progression has not been observed will be censored at the last time known to be alive and without a disease progression; i.e. censored at the latest progression assessment date or disease recurrence assessment date if the patient has not had a recurrence, progression or death. However, if the patient experiences a progression or dies immediately after two or more consecutive missed visits, the patient will be censored at the time of the last progression assessment prior to the two missed visits.

3.2.5. Time to First Subsequent Therapy or Death (exploratory)

Time to first subsequent therapy or death (TFST) is defined as the time from the date of randomisation to the earlier of the date of first subsequent anti-cancer therapy or procedure start date following study treatment discontinuation, or death (i.e. date of first subsequent anti-cancer therapy/procedure/death or censoring – date of randomisation + 1). Any patient not known to have had a first subsequent therapy/procedure or not known to have died at the time

of the analysis will be censored at the last known time to have not received first subsequent therapy; i.e. the last follow-up visit where this was confirmed. If a patient terminated the study for a reason other than death before first subsequent therapy, such patients will be censored at the earliest of their last known to be alive and termination dates. Patients not receiving randomised treatment would have TFST calculated as time from date of randomisation to the initial therapy or death.

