8.4.1.4 Time to first subsequent therapy or death (exploratory)

Time to first subsequent therapy (TFST) or death is defined as the time from the date of randomisation to the earlier of the date of anti-cancer therapy or procedure start date following

study drug discontinuation, or death. Any patient not known to have had a subsequent therapy/procedure or not known to have died at the time of the analysis will be censored at the last known time to have not received subsequent therapy; i.e., the last follow-up visit where this was confirmed.

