8.4.1.5 Time to second subsequent, therapy or death (exploratory)

Time to second subsequent therapy (TSST) or death is defined as the time from the date of randomisation to the earlier of the date of second subsequent anti-cancer therapy or procedure start date following study drug discontinuation, or death. Any patient not known to have died at the time of the analysis and not known to have had a second subsequent therapy/procedure will be censored at the last known time to have not received second subsequent therapy, i.e., the last follow-up visit where this was confirmed.

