3.2.6. Time to Second Subsequent Therapy or Death (exploratory)

Time to second subsequent therapy or death (TSST) is defined as the time from the date of randomisation to the earlier of the date of second subsequent anti-cancer therapy or procedure start date following study treatment discontinuation, or death (i.e. date of second subsequent anti-cancer therapy/procedure/death or censoring – date of randomisation + 1). Any patient not known to have died at the time of the analysis and not known to have had a second subsequent therapy/procedure will be censored at the last known time to have not received second subsequent therapy; i.e. the last follow-up visit where this was confirmed. If a patient terminated the study for a reason other than death before second subsequent therapy, such patients will be censored at the earliest of their last known to be alive and termination dates. Patients not receiving randomised treatment would have TSST calculated in the same way, i.e. time from date of randomisation to the subsequent therapy or death.

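### The TFST censoring sentence says 'or' where the event definition and the TSST rule need 'and', so read literally it censors patients who have had a TFST event

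*SAP*

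**What the plan says.** **Event.** SAP 3.2.5 measures TFST from randomisation "to the earlier of the date of first subsequent anti-cancer therapy or procedure start date following study treatment discontinuation, or death". Protocol 8.4.1.4 defines it in the same way.

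**Censoring.** The next sentence of SAP 3.2.5 applies to "Any patient not known to have had a first subsequent therapy/procedure or not known to have died at the time" of the analysis. Such a patient "will be censored at the last known time to have not received first subsequent therapy", which the SAP explains as the last follow-up visit at which this was confirmed. Protocol 8.4.1.4 has the same construction: "not known to have had a subsequent therapy/procedure or not known to have died at the time of the analysis".

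**The parallel endpoint.** For TSST (time to second subsequent therapy or death), SAP 3.2.6 censors "Any patient not known to have died at the time of the analysis and not known to have had a second subsequent therapy/procedure", and Protocol 8.4.1.5 agrees: "Any patient not known to have died at the time of the analysis and not known to have had a second subsequent". Both join the two conditions with 'and'.

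**Use.** SAP 4.3.7.3 reports TFST in the overall population with the DFS model: a hazard ratio with 95% CI, medians and a Kaplan-Meier plot. It calls the endpoint supportive, with no multiplicity adjustment and no formal comparison. SAP section 6, which lists changes from the protocol, does not mention the TFST rule.

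**The concern.** For an endpoint that is the earlier of two things, a patient is event-free only if neither has happened. The TFST sentence repeats the negation on each side of 'or', so missing either one is enough to be censored. That reverses the definition given one sentence before it.

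The censoring date adds to the problem. A living patient who started a new treatment would be censored at the last visit before that treatment, so the event itself would trigger the censoring. A patient who died untreated would be censored at the last visit at which no treatment was confirmed, before the death.

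At stake is whether the derivation can be programmed from the text. Two programmers working independently from SAP 3.2.5 could build different TFST datasets, one from the definition and one from the censoring sentence. A programmer who gets it right has to depart from the approved wording without a documented reason. The Protocol cannot settle the matter, because it carries the same word.

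**Working it through.** **1. The rule against the definition.** There are four patient types at the time of analysis:

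| Subsequent therapy | Died | TFST event by definition | Censored under 'or' | Censored under 'and' |
|---|---|---|---|---|
| No | No | No | Yes | Yes |
| No | Yes | Yes | Yes (wrong) | No |
| Yes | No | Yes | Yes (wrong) | No |
| Yes | Yes | Yes | No | No |

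Under 'or', two of the four types are misclassified, and only patients with both therapy and death remain as events. Under 'and', none is misclassified and the rule matches TSST.

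**2. Size at the January 2020 cut-off.** The plan gives no TFST event count, so there is no figure to reproduce. These inputs show scale only:

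- Deaths, overall population: 29, of which 9 on osimertinib and 20 on placebo (Protocol 1.4). Check: 29/682 = 4.25%, which agrees with the stated 4.3%.
- DFS events, overall population, at IDMC7: 196 (SAP section 7, Table 7). The SAP says that exact counts are to be confirmed after database lock and unblinding.

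*Cap under the literal rule.* An event needs both therapy and death, so TFST events cannot exceed the number of deaths, 29. The cap is reached only if every patient who died had also started a subsequent therapy.

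*Living patients with recurrence.* A DFS event is recurrence or death. At most 29 of the 196 patients with a DFS event had died, so at least 196 − 29 = 167 had recurred and were alive.

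*Events under 'and'.* Let *s* be the share of those 167 who had started a subsequent therapy. The documents do not give *s*, so it is an assumption. With all 29 deaths counted, events = 29 + 167*s*. The proportion lost under the literal rule is then at least 167*s* / (29 + 167*s*).

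| Assumed *s* | Events under 'and' | Literal cap | Minimum proportion lost |
|---|---|---|---|
| 25% | 70.75 (about 71) | 29 | 41.75/70.75 = 59% |
| 50% | 112.5 (about 113) | 29 | 83.5/112.5 = 74% |
| 75% | 154.25 (about 154) | 29 | 125.25/154.25 = 81% |
| 100% | 196 | 29 | 167/196 = 85% |

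The losses are minimum values for each *s*, because any patient who died untreated would also be lost. The 196 in the last row is not a ceiling: SAP 3.2.1 allows for anti-cancer therapy before recurrence, and such patients would add to TFST events under 'and'.

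**The case against.** The best defence is that SAP 3.2.5 largely explains itself. The preceding sentence defines the event as the earlier of therapy or death, and its formula lists therapy, procedure or death as the end date. The censoring date fits a patient who has not been treated. The termination rule concerns patients who leave before a first subsequent therapy, and the closing sentence again ends TFST at initial therapy or death. Together with the 'and' in the next section, this leaves no real doubt about intent. It is a drafting slip, not a choice of method, and nothing in the documents suggests that it was programmed literally. TFST is exploratory and outside the testing hierarchy. The extension protocol describes only OS analyses from here on, with formal testing complete (Protocol 8.8).

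All of that stands, and it keeps the point small. It does not make the sentence right. The censoring sentence is the operative instruction for an endpoint reported with a hazard ratio, and no other passage corrects it.

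A reader might go further and infer that TFST would lose nearly all its events, that the losses would be mostly placebo patients, and that the hazard ratio would be meaningless. The documents do not support this. They give no count of patients starting subsequent therapy, overall or by arm. The minimum loss ranges from 59% to 85% over the shares tried above and would be lower for a smaller share. The overall DFS hazard ratio of 0.20 (Protocol 1.4) makes a placebo excess plausible, but that is an inference and not a reported figure.

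**Conclusion.** Wrong as written, minor. The TFST censoring sentence in both documents contradicts the event definition beside it and the TSST rule that follows it. This conclusion rests on the wording alone and needs no assumption.

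The size is less certain. The cap of 29 events holds only at the January 2020 cut-off. Protocol 8.7 allows TFST to be reported again at later DFS analyses, when more deaths would have accrued. The figure of at least 167 living patients with recurrence depends on a provisional DFS count, and the proportion of events lost depends on an assumed share treated. A real effect would arise only if the sentence had been programmed literally, against the definition. No alpha, power, primary or secondary conclusion depends on TFST.

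**What to change.** In SAP 3.2.5 and Protocol 8.4.1.4, replace 'or' with 'and' in the censoring sentence, so that only a patient with neither a subsequent therapy or procedure nor death is censored, as for TSST.

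Also confirm that the programmed TFST derivation already does this, for the reporting that followed IDMC7 and for any later update. If it does, a short note to file would record that the reported results followed the definition.

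The cost is one word in each document plus a check of one derived dataset. Both are controlled documents, so the wording can wait for the next revision; the programming check need not.

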3.2.6. Time to Second Subsequent Therapy or Death (exploratory)

Time to second subsequent therapy or death (TSST) is defined as the time from the date of randomisation to the earlier of the date of second subsequent anti-cancer therapy or procedure start date following study treatment discontinuation, or death (i.e. date of second subsequent anti-cancer therapy/procedure/death or censoring – date of randomisation + 1). Any patient not known to have died at the time of the analysis and not known to have had a second subsequent therapy/procedure will be censored at the last known time to have not received second subsequent therapy; i.e. the last follow-up visit where this was confirmed. If a patient terminated the study for a reason other than death before second subsequent therapy, such patients will be censored at the earliest of their last known to be alive and termination dates. Patients not receiving randomised treatment would have TSST calculated in the same way, i.e. time from date of randomisation to the subsequent therapy or death.

3.2.7. Brain Metastases

ADAURA population consists of patients with EGFR Mutation Positive Stage IB-III A NSCLC and brain/CNS metastasis present at baseline is an exclusion criterion. On study, the appearance of brain cancer metastases will be those recorded on the CRF (e.g. DISREC) as Brain/CNS at disease recurrence (not including those recorded as Other CNS).

3.2.8. Health-Related Quality of Life

Patient-reported HRQoL will be assessed using the SF-36 questionnaire.

3.2.8.1. SF-36 v2 (standard)

The SF-36 includes eight domains: Physical Functioning (PF); Role Limitations-Physical (RP), Vitality (VT), General Health Perceptions (GH), Bodily Pain (BP), Social Function (SF), Role Limitations-Emotional (RE), and Mental Health (MH). These can be summarised into two summary scores: The Physical Component Summary (PCS) and Mental Component Summary (MCS). Final scores for each scale range from 0-100 with higher scores indicating better health. The general population has a mean score of 50 with a standard deviation (StdDev) of 10.

The absolute values and change from baseline will be calculated for each domain and summary scale at each scheduled post-baseline assessment. The visit response to the SF-36 at each assessment will also be categorised as improved, worsened and stable based on the

changes from baseline using the criteria for a minimum clinically important difference as shown in Table 3.

Table 3 SF-36 Visit Response Categories

Score	Visit response		
	Improved	Worsened	Stable
PCS	$\geq + 3.1$	$\leq - 3.1$	Otherwise
MCS	$\geq + 3.8$	$\leq - 3.8$	Otherwise
PF	$\geq + 3.5$	$\leq - 3.5$	Otherwise
RP	$\geq + 3.2$	$\leq - 3.2$	Otherwise
BP	$\geq + 4.5$	$\leq - 4.5$	Otherwise
GH	$\geq + 5.7$	$\leq - 5.7$	Otherwise
VT	$\geq + 5.5$	$\leq - 5.5$	Otherwise
SF	$\geq + 5.0$	$\leq - 5.0$	Otherwise
RE	$\geq + 3.8$	$\leq - 3.8$	Otherwise
MH	$\geq + 5.5$	$\leq - 5.5$	Otherwise

Time to deterioration of HRQoL is defined as time from date of randomisation to the date of first clinically important worsening confirmed at the subsequent assessment, or death (by any cause) in the absence of a clinically important worsening, provided death occurs within two assessment visits of the last assessment where HRQoL could be evaluated and regardless of whether the patients withdraws from randomised therapy or receives another anticancer therapy prior to symptom deterioration.

3.2.8.2. Compliance

Summary measures of overall compliance and compliance over time will be derived for patient-reported HRQoL. This will be based upon:

- Received questionnaire = a questionnaire that has been received and has a completion date and at least one individual item completed.
- Expected questionnaire = a questionnaire that is expected to be completed at a scheduled assessment time e.g. a questionnaire from a patient who has not died, is not lost to follow-up or withdrawn from the study at the scheduled assessment time but excluding patients in countries with no available translation. Date of study discontinuation will be mapped to the nearest visit date to define the number of expected forms.

- Evaluable questionnaire = a questionnaire with a completion date and at least one subscale that is non-missing.
- Overall PRO compliance rate is defined as: Total number of evaluable questionnaires across all time points, divided by total number of questionnaires expected to be received across all time points multiplied by 100.
- Overall patient compliance rate is defined for each randomised treatment group as: Total number of patients with an evaluable baseline and at least one evaluable follow-up questionnaire (as defined above), divided by the total number of patients expected to have completed at least a baseline questionnaire multiplied by 100.

Compliance over time will be calculated separately for each visit, including baseline as the number of patients with an evaluable questionnaire at the time point (as defined above), divided by number of patients still expected to complete questionnaires. Similarly, the evaluable rate over time will be calculated separately for each visit, including baseline, as the number of evaluable questionnaires (per definition above), divided by the number of received questionnaires.

3.2.9. Health Care Resource Use (exploratory)

The Healthcare Resource Use Module will be completed by the investigational site for any healthcare resource use between visits. The site will ask patients for any health resource use between visits (i.e., excluding routine follow-up clinic visits associated with the clinical trial but including both planned and unplanned admissions) during treatment period.

To investigate the impact of treatment and disease on health care resource, the following variables will be captured:

- Planned and unplanned hospital attendances beyond trial protocol mandated visits (including physician visits, emergency room visits, day cases and admissions)
- Primary sign or symptom the patient presents with
- Length of hospital stay
- Length of any time spent in an intensive care unit (ICU)

Where admitted overnight, the length of hospital stay will be calculated as the difference between the date of hospital discharge (or death date) and the start date of hospitalisation or start of study drug if the start of study drug is after start date of hospitalisation (length of hospital stay = end date of hospitalisation – start date of hospitalisation + 1). Patients with missing discharge dates will be calculated as the difference between the last day with available data and the start date of hospitalisation. The length of ICU stay will be calculated using the same method.

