3.1.3. Handling Missing Data

In general, other than for partial dates, missing data will not be imputed and will be treated as missing, unless otherwise specified.

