4.2. General Principles

Continuous data will be summarised using descriptive statistics (number of observations, mean, standard deviation, median, 25th and 75th percentiles, minimum, and maximum). Frequencies and percentages will be used for summarising categorical (discrete) data.

Confidence intervals (CIs), when presented, will generally be constructed at the 95% confidence level. For binomial variables, the normal approximation methods will be employed unless otherwise specified.

A month is defined to be 30.4375 days.

Data will be presented in data listings by patient identifier and treatment arm.

All summaries will be presented by treatment group unless otherwise specified.

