4.3.7.3. Exploratory Outcomes

Healthcare Care Resource Use

Health Care Resource Use data (i.e. the hospital admission details including type of attendance and primary symptom for admission) will be listed and presented using frequencies and percentages. The duration of admission/attendance and duration of intensive care unit (ICU)/high dependency unit (HDU) stay will be summarised using descriptive statistics, based on the FAS. It will summarised from randomisation and up to and including treatment discontinuation.

Analysis of Progression-Free Survival

Progression status at the time of analysis by treatment arm will be categorised into radiological, symptomatic, other progression or death, with reasons for censoring also summarised accordingly. PFS data will be analysed for the overall population using the same methodology and model as for the analysis of DFS with the exception that the sensitivity, subgroup and exploratory analyses will not be performed. The HR for the treatment effect together with its 95% CI will be presented. In addition, medians and Kaplan-Meier plot will be presented by treatment arm to support the analysis. It will be summarised per treatment arm, but no formal comparisons will be made. No multiplicity adjustment will be applied as this is viewed as a supportive endpoint. Time from randomisation to progression will be summarised by treatment arm.

Post-Relapse Outcomes

TFST and TSST will be summarised for the overall population using the same methodology and model as for the analysis of DFS with the exception that the sensitivity, subgroup and

exploratory analyses will not be performed. The HR for the treatment effect together with its 95% CI will be presented. In addition, medians and a Kaplan-Meier plot of the time to the start of subsequent therapy will be presented by treatment arm and the time between recurrence and starting subsequent therapy will be assessed. This will be summarised per treatment arm, but no formal comparisons will be made. No multiplicity adjustment will be applied as this is viewed as a supportive endpoint.

In patients who received a subsequent anti-cancer therapy, a summary table of first (and second) subsequent anti-cancer therapies by treatment arm will be provided, as well as response to first subsequent anti-cancer therapy by treatment arm (if available).

A summary of the number of patients prematurely censored will also be produced.

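### Every hospital or ICU stay with a missing discharge date is run to an undefined last data day, even when the patient had already left hospital

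*SAP*

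**What the plan says.** For a complete overnight stay, SAP 3.2.9 counts both end days ("length of hospital stay = end date of hospitalisation – start date of hospitalisation + 1"). Date of death can replace discharge, and the start of study drug replaces admission if it is later. For incomplete stays it adds: "Patients with missing discharge dates will be calculated as the difference between the last day with available data and the start date of hospitalisation". For intensive care: "The length of ICU stay will be calculated using the same method".

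SAP 4.3.7.3 says the durations "will be summarised using descriptive statistics, based on the FAS", and then sets a window: "It will summarised from randomisation and up to and including treatment discontinuation". Under SAP 4.2, descriptive statistics for continuous data include the mean, SD and maximum as well as the median and quartiles.

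The SAP's general position on missing data, in 3.1.3, is different: "In general, other than for partial dates, missing data will not be imputed and will be treated as missing, unless otherwise specified". In 3.1.3.1, a wholly missing end date for an adverse event or a concomitant medication is left unimputed.

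**The concern.** The rule makes sense for a patient who is still an in-patient when data collection stops. As written, it covers every missing discharge date. Death already serves as an end date in the main formula, so the rule falls mainly on survivors. A survivor who attended a later clinic visit had usually gone home, and for that patient the last data day says nothing about when the stay ended.

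Comparing resource use between arms is an exploratory objective (Protocol 2.4). Protocol 5.3.4.4 collects length of stay, including intensive care, for economic evaluation. That work rests on means, and a mean is the statistic most easily moved by a few very long false stays.

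**Working it through.** The plan gives no length of stay, admission rate or missing-date rate, so there is no figure of its own to reproduce. The check is date arithmetic on the stated rule.

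**Inputs from the documents.** Treatment lasts at most 156 weeks, which is 156 × 7 = 1,092 days (Protocol synopsis). On-treatment visits are 12 weeks apart from week 12 (Protocol Table 1). Recurrence follow-up runs to week 264 and then yearly (Protocol 1.6).

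**Assumed inputs.** The admission week, the true length of stay, the number of stays and the number with a missing discharge date.

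**1. Length given to one stay.** Formula: imputed stay = last data day − admission day. For admission at week 4 and last data at week 156, this is (156 − 4) × 7 = 1,064 days, or 1,064 / 365.25 = 2.9 years. Other cases, in days:

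| Admission | Last data at next 12-weekly visit | Last data at week 156 | Last data at week 264 |
|---|---|---|---|
| Week 4 | 56 | 1,064 | 1,820 |
| Week 24 | 84 | 924 | 1,680 |
| Week 100 | 56 | 392 | 1,148 |
| Week 150 | 42 | 42 | 798 |

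The true length of stay does not enter the formula. A 5-day admission receives these values.

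**2. Effect on the mean.** Assume a true mean of 7 days and k stays out of n imputed at 500 days. Mean = [7(n − k) + 500k] / n.
- n = 100, k = 1: (693 + 500) / 100 = 11.9 days (+70%).
- n = 100, k = 3: (679 + 1,500) / 100 = 21.8 days (+211%).
- n = 50, k = 1: (343 + 500) / 50 = 16.9 days.

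**3. Effect on SD and median.** Assume every true stay is 5 days and one is imputed at 1,064 days. Mean = [5(n − 1) + 1,064] / n and SD = (1,064 − 5) / √n.
- n = 20: mean 58.0, SD 237 days.
- n = 50: mean 26.2, SD 150 days.
- n = 100: mean 15.6, SD 106 days.

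The maximum is 1,064 days and the median stays at 5 days in all three.

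**4. ICU stay against hospital stay.** Suppose a patient is admitted straight to intensive care on day 100, is discharged from hospital on day 110, has no ICU end date and has last data on day 600. The hospital stay is 110 − 100 + 1 = 11 days. The ICU stay is 600 − 100 = 500 days. Nothing in the SAP prevents this.

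**The case against.** The strongest reply is that the last data day is undefined. If it meant the last record for that admission, the excess would be small. If the window in SAP 4.3.7.3 also cuts off the imputed end date, the ceiling is about 156 weeks. Both points are fair, and they limit the size of the problem. But the SAP states neither, and with last data at only the next 12-weekly visit the table still gives 42 to 84 days.

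Missing dates may also be few. Resource data come mainly from the medical record (Protocol 5.3.4.4), source data are verified (Protocol 9.2) and missing data are queried (Protocol 9.4). That is a good reason to expect low counts, and it is why the magnitudes above are illustrations only.

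The missing-date sentence does not repeat the +1. It reuses the wording of the complete-stay rule and may inherit its definition, so this is at most a one-day ambiguity.

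A reader might infer that the rule inflates resource use on osimertinib, because randomised treatment stops at recurrence (Protocol 3.10) and recurrence or death was far less frequent on osimertinib (DFS hazard ratio 0.20 overall, Protocol 1.4). The documents do not support stating that as fact. It needs similar missingness in both arms and an end day tied to time on treatment. If any record counts, both arms continue in follow-up after treatment stops (Protocol 1.6), and time on treatment no longer sets the end day. No arm-specific counts are given.

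**Conclusion.** The point holds as a minor one. The stated rule gives wrong values for discharged patients with a missing date, and it departs from the SAP's own default of leaving such data missing. On the plain reading, the false stay runs from weeks to about three years, or about five years (1,820 days) if follow-up to week 264 counts. An ICU stay can exceed its hospital stay.

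The harm is confined to the mean, SD and maximum of an exploratory, untested endpoint, and to any economic work that uses those means. How much they move depends on the number of missing discharge dates, which the documents do not give. The direction of any difference between arms is uncertain.

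**What to change.** Amend SAP 3.2.9 as follows.

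- Where the discharge date is missing from the resource-use module, take it from the SAE form, which collects it (Protocol 6.3.3). This source is partial. Planned admissions for pre-existing illness (Protocol Appendix B) and events unequivocally due to recurrence (Protocol 6.3.8) need not be reported as adverse events.
- Apply the last-data-day rule only to patients still in hospital at data cut-off, define that day, and state whether treatment discontinuation truncates it.
- In all other cases set the length to missing, and report the number of such stays by arm.
- Use a cap at the next attended visit as a sensitivity analysis only. With visits 12 weeks apart, ending the stay on the day before the next visit can still give about 83 days. Three such stays in 100 would move an assumed 7-day mean to (679 + 249) / 100 = 9.3 days (+33%).
- Bound the ICU end date by hospital discharge, and state that the same +1 convention applies throughout.

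For outputs already produced, check whether any stay was imputed under the current rule before using the means.

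The cost is a few sentences in the SAP and a little more derivation code. The downside is that a few stays will have no duration.
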